Resourcefulness is an “acquired repertoire of skills and behaviors necessary for the successful execution of self-control behavior.”^{19 p.26} These skills are learned throughout life by informal training or may be taught in cognitive behavioral programs and include the belief that one is able to cope effectively despite adversity.¹⁹ Skills of self-instruction, problem-solving, belief in coping effectiveness are used to control the effects of disturbing feelings, thoughts and sensations on performance of daily tasks.¹⁹ Zauszniewski’s²⁰ model includes personal resourcefulness (self-help) and social resourcefulness (help-seeking) that are beneficial for maintaining healthy physical and psychological functioning across the lifespan. Resourcefulness training (RT) includes teaching positive self-talk, problem-solving and priority setting.¹⁵

Empirical evidence indicates that resourcefulness is a significant predictor of quality of life for non-caregivers/caregivers.^{19, 23} **Parent outcomes** are conceptualized as absence of depressive symptoms, positive family functioning, better self-assessed health. **Depressive symptoms** include depressed mood and feelings of helplessness and hopelessness.¹⁰ Greater resourcefulness is a significant predictor of a decreased level of depressive symptoms.²⁵ Conversely, less resourcefulness contributed to perceptions of worse family functioning in grandmothers raising grandchildren.¹⁷ **Family functioning** is a parent’s perception and level of satisfaction with relationships between the family and individuals as well as subsystems and the community. **Self-assessed health** is the mother’s perception of her health and includes both physical and psychological well-being.²⁷ Based on the theoretical and empirical literature, the study model proposes that contextual factors, process regulators, and resourcefulness all directly affect quality of life outcomes.

Inclusion and Exclusion Criteria

1. Describe how individuals will be screened for eligibility.
2. Describe the criteria that define who will be **included** in your final study sample.

	Inclusion
1.	Parents who are at least 18 years of age
2.	Parents caring for a child age 16 years and younger at home who is technology-dependent (Group 1 mechanical ventilators; Group 2 intravenous nutrition/medication; Group 3 respiratory or nutritional support);
3.	Able to speak, write and understand English.
4.	

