3. Describe the criteria that define who will be **excluded** in your final study sample.

	Exclusion
1.	Parents of children with cancer.
2.	
3.	
4.	

Number of Research Participants

1. *Indicate the target number of research participants to be accrued locally.*
2. *If this is a multi-site study, indicate the total number of research participants to be accrued across all sites.*

For this study, 123 subjects are expected to be enrolled.

Vulnerable Populations

1. *Indicate specifically if you will include each of the following special populations by checking the appropriate box:*

- Adults unable to consent**
- Minors (infants, children, teenagers)**
 - Wards of the state
 - Foster Children
- Pregnant Women**
- Neonates**
- Neonates of Uncertain Viability**
- Employees of CWRU or UHHS**
- Prisoners**
- Illiterate Individuals**
- Non-English Speaking**
- University Students**

2. *If the research involves individuals that are included in a vulnerable population, describe the additional safeguards included to protect the rights and welfare of the individuals for each population indicated.*

We will include pregnant women or women who become pregnant while enrolled in the study because many mothers of technology-dependent children are in the child-bearing years. They will be told that they are volunteers and can leave the study at any time. While we will not be directly asking the children any questions we will be asking their parent to describe things such as what type of technological equipment they use and questions about their eating and sleeping. Therefore, we have a procedure for asking about the child's assent if they are 7 years or older.

3. *If excluding pregnant women, illiterate or non-English speaking individuals, provide a scientific rationale for the exclusion. Inconvenience or cost is not an acceptable rationale.*

We will exclude illiterate or non-English speaking individuals due to the amount of reading, writing that must be done as part of the intervention and follow up data collection. Also, our instruments have not been translated into another language.

Recruitment Methods

1. *Describe the source of the research participants.*
2. *Describe the methods that will be used to identify potential research participants.*

3. *Justify the feasibility of recruiting the required number of suitable research participants within the agreed recruitment period. For example, how many potential research participants do you have access to?*

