4. *Describe when, where, and how potential research participants will be recruited.*
5. *Describe materials that will be used to recruit research participants.*

Participant recruitment and enrollment: RB&C Specialty Clinics (Pulmonary, Gastroenterology, Trach/Vent, Comprehensive Care) and Family Learning Center who are associated with this study will distribute the IRB approved study flyer or brochure that contains study staff contact information to potential participants. Potential participants can then call the study staff with questions or to volunteer.

We will also check EMR (All Scripts, Soarian, Whiteboard) and do prescreening for potential participants by checking pulmonology outpatient clinic schedules. We will come to clinic to meet those who meet eligibility to invite them to hear more about the study. If they are interested the study team member will ask about a date/time for appointment. If they are unsure of their schedule we will ask for the best way to contact them to set up appointment at a time/place of their choosing like their home or a library.

Another recruitment strategy will be to post IRB approved study flyers in RB&C/UH Common areas, Family Learning Center and Family Resource Center as well as the RB&C inpatient units that admit technology-dependent children and their corresponding family lounge bulletin boards or posting areas as well as clinic rooms. This will help to gain visibility of our study to enhance recruitment efforts.

We will also distribute our brochures and flyers at family health fairs, specialty organization meetings, support groups, parenting events and gatherings that are frequented by parents of technology-dependent children in Northeast Ohio community to promote awareness of the study by community. In addition, they will be distributed to organizations such as United Cerebral Palsy, Achievement Center of Cleveland, Health Departments that provide services for technology-dependent children and their families. We will also place ads in regional Parenting Magazines and Facebook to help promote recruitment.

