In addition to the informational letter that will be sent to potential participants identified by study sites, clinic providers will hand out a flyer that gives the study contact information. It will be up to the parent to then contact the study staff to ask questions or to volunteer to participate. The flyer will help to advertise the study.

Potential participants will also be recruited using a Facebook page and Twitter. Both forms of social media will assist in the distribution of the IRB approved study flyer to enhance recruitment efforts. We will include limits of Northeast Ohio since data collection is done face-to-face.

1. A Facebook page will be developed to post the flyer and increase awareness regarding the study. A "Friend" request will be sent to other parent caregiver organizations with Facebook sites likely to include eligible participants asking for permission to post the IRB approved study flyer on their Facebook page and let their members know about the study. The informational letter to be sent with the "Friend" request is attached.

2. Tweets are limited to 140 characters or less. Tweets will be used and an image of the study flyer will be attached with the tweets. As we find more followers and parent caregiver organizations, we will tag them in our tweets to increase our visibility. "@" will be used to tag or mention an organization and "#" will be used to categorize the tweets. Here are examples of tweets:

@resourceTD needs your help to test a way to reduce stress in #parent #caregivers of technology-dependent children in Northeast Ohio!
 @resourceTD Are you a #parent #caregiver of a child who uses #oxygen #ventilator or #gtube medical technology in Northeast Ohio?
 @fpbnursing researching how to reduce stress in #parent #caregivers of children on medical technology in Northeast Ohio. Please contact us to help!

Following this assessment and affirmation of the mother’s willingness to participate the parent will be queried as to the child’s receipt of the assent letter and confirm the child’s assent to have the mother participate in the study. With the above confirmed, the parent will be asked to set up an appointment with the research staff at a mutually convenient time and location. If the potential participant does not contact the research team in 1 week, a phone call will be made to invite them to volunteer for the study.

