An appointment will be made to meet with the potential participant at the time and place of their choosing (their home, public library, their place of employment, child's therapy center such as United Cerebral Palsy Center, Dahm's Clinical Research Unit) to obtain informed consent. Study personnel will obtain informed consent and explain to the potential participant that he/she is being asked to provide consent for participation in a research study. It will be explained that participation is totally voluntary and their choice regarding participation will not affect their child's care in any way. Additionally, parents will be given a description of the study, procedures, risks and benefits, confidentiality and voluntary nature of the study including the option to withdraw at any time. Following this discussion, parents will be given the consent form to review. Parents will be given the opportunity to take a few minutes alone to review the written consent form and to make a decision regarding participation. No data collector that has clinic contact with the potential participant will engage in their recruitment so there is no undue influence to participate. Parents will be

assured that none of the data obtained will be communicated to any healthcare personnel at the outpatient clinic or hospital site. A study brochure will be given to participants.

Setting

1. *Describe the sites or locations where your research team will conduct the research.*
We will conduct the research data collection at a private place of the parent’s choosing such as their home, library. Our study office is located in the FPB School of Nursing, CWRU.

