Research Design. A quasi-experimental RCT design with random assignment will be used to test the efficacy of a Resourcefulness Training (RT) intervention compared with an attention control group in mothers and fathers of technology-dependent children. All participants will receive a face-to-face visit from study staff for the T1 data collection. In addition, the intervention group will receive individually tailored RT web based instruction via an approximately 30 minute video that provides details on each of the 8 resourcefulness skills with short examples of application, instruction on journal writing to practice and reinforce use of resourcefulness skills, access to video tapes of parents describing application of resourcefulness skills in the care of their technology-dependent child. Parents will be asked to provide their email address so that we may send them invitation for access to the website that they may visit at any time to access the video tapes. Data will also be collected face-to-face at 3 months (T3) and 6 months (T4) post-intervention. At 6 weeks parents will be emailed a link to the REDCap survey for Time 2 data collection and contacted by phone for SF-12 survey with email reminders. Open-ended questions following their final data collection appointment will allow mothers/fathers to discuss feasibility, acceptability, and fidelity of this intervention and suggestions for potential modification of the intervention and follow up procedures. For this study, 99 female participants and 24 male participants are expected to be enrolled that takes into account 10% attrition.

Measures/Instruments.

The **Depressive Cognition Scale** an 8-item scale ($\alpha = .75$), will measure depressive thought patterns that may lead to depression.⁸ Responses on a 6-point scale range from strongly agree (5) to strongly disagree (0) with a score range 0-40. Items include depressive cognitions such as hopelessness and worthlessness; higher scores indicate more depressive cognitions.

The **Resourcefulness Scale**, a 28-item scale ($\alpha = .85$), will assess both personal (16 items) and social (12 items) resourcefulness.⁹ Responses on a 6-point scale range from extremely descriptive (5) to not descriptive (0) with a score range 0-140; higher scores indicate greater resourcefulness. Construct validity was assessed using confirmatory factor analysis.

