answer the interview and study questions. Parents will be told that they may choose to take a break at any point during the interview. The amount of time required for participation in the study may also be viewed as an inconvenience. A potential emotional risk during the interview is that recalling information regarding their child’s course of illness and home management difficulties may make some parents uncomfortable. Participants will be told that they may withdraw from the study at any time. The interviewer will be vigilant to assess the participant’s discomfort. Participants experiencing considerable discomfort will be asked if they wish to stop the interview and will be given supportive assistance by the interviewer. The mother/father will then be given the number of United Way First Call (211) to access on call mental health professional services in their local area or Cuyahoga County 24-Hour Mental Health Crisis Information and Referral [contact]). If any participant is noted to have a level of depressive symptoms above the recognized cutoff of 16 on the Center for Epidemiological Studies (CES-D) measure she/he will be told of the findings and given an information sheet regarding accessing mental health care resources such as United Way First Help (phone 211) or the Cuyahoga County 24-Hour Mental Health Crisis Information and Referral [contact]). Any participant noted to have a score of 23 or above on the CES-D will be assessed for imminent risk of suicide by asking if they have had any thoughts of harming themselves in any way or perhaps killing themselves. If the answer to any portion of the question is “yes” the participant will be told of a concern for their safety and the necessity for the interviewer to contact the Mobile Crisis Team from the Cuyahoga County 24-Hour Mental Health Crisis, Information and Referral Hotline immediately. The risks and discomforts involved are reasonable because the risks are temporary and can be minimized by the above procedures. In addition, the discomfort is no more than what the participant might experience in her/his daily life.

**3. Describe: Procedures to decrease risk- See above
Drugs/Devices; Source Records- Not Applicable**

- Procedures performed to lessen the probability or magnitude of risks*

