3. *If applicable, indicate which procedures may have risks to an embryo or fetus should the research participant or their partner be or become pregnant. **Not applicable.***
4. *If applicable, describe the risks to others who are not research participants. **Not applicable.***
5. *Describe the availability of medical or psychological resources that research participants might need. **See above.***

Provisions to Protect the Privacy Interests of Research Participants

Describe the steps that will be taken to protect research participants’ privacy interests. (consider issues such as physical space, proximity to other, and participant preferences)

To maintain participant privacy, all interviews will be conducted in a private area in a place of the mother’s/father's choosing such as her/his home, public library, place of employment or the Dahms Clinical Research Center. Privacy will be maintained as well in the procedures for identifying participants as described above. Participants will be mailed an introductory letter prior to study staff making telephone contact.

Facebook and Twitter will be used to post the IRB flyer about the study. A "Friend" request will be sent to parent caregiver organizations who have members likely to meet inclusion criteria along with an introductory letter about our study and the request to post our recruitment flyer. The organization can make a decision to accept or reject the request to post our study flyer. Potential participants reached through either Facebook or Twitter would then self-identify and voluntarily contact us to hear more about the study and decide on participation. When they contact the study staff they will be screened for eligibility including residence within Northeast Ohio for face-to-face data collection.

A digital audio recording device will be used during parent interviews that might be regarded as an invasion of privacy. The reason for use of the audio recording device is to allow the data collector to focus on the interview and probes without the encumbrance of taking notes and risk missing essential portions of the parent’s response. Using the recording device will therefore add

to the richness of the interview data for analysis. The participant’s name will not be mentioned on the digital recording. The recording device and any memory cards will be kept in a locked filing cabinet when not in use.

Potential Benefit to Research Participants

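### After a yes on self-harm, the only crisis contact named for the interviewer is a Cuyahoga County service, although parents are recruited across Northeast Ohio

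*Combined protocol and SAP*

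**What the plan says.** The crisis step is in Study Design, Procedures and Timeline (item 2) and is repeated in Risks to Research Participants (item 1). A CES-D of 23 or above leads to a question about self-harm or suicide. If any part is answered yes, the parent is told of a safety concern and of "the necessity for the interviewer to contact the Mobile Crisis Team from the Cuyahoga County 24-Hour Mental Health Crisis, Information and Referral Hotline immediately". Neither section names another service at this step.

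The area from which parents come is described elsewhere:

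- Inclusion and Exclusion Criteria: parents must be adults who can use English, and must be "Parents caring for a child age 16 years and younger at home who is technology-dependent". The one listed exclusion is "Parents of children with cancer". There is no residence or county criterion.
- Recruitment Methods: brochures and flyers go to events and "gatherings that are frequented by parents of technology-dependent children in Northeast Ohio community". For social media the protocol says "We will include limits of Northeast Ohio since data collection is done face-to-face".
- Provisions to Protect the Privacy Interests of Research Participants: people who respond through Facebook or Twitter are "screened for eligibility including residence within Northeast Ohio for face-to-face data collection".
- Recruitment Methods, on the consent appointment: staff will "meet with the potential participant at the time and place of their choosing", with home and workplace among the examples. The Setting section likewise leaves the place of data collection to the parent.

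**The concern.** The service that the interviewer must contact carries one county's name, while the trial recruits from a wider region and visits parents at places they pick. An interviewer sitting with an at-risk parent in another county would have a written instruction that may not fit the place, and no written substitute. What is at stake is how quickly the right service is reached. The protocol also calls its risks reasonable partly because these procedures minimise them, so the crisis step should fit every parent the trial may enrol. The treatment comparison is not involved.

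**Working it through.** No arithmetic decides this point. It rests on setting the text side by side.

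**Step 1: the three distress steps, as written in both sections.**

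| Trigger | Who would use the contact | 211 offered | Cuyahoga County service named |
|---|---|---|---|
| Considerable discomfort in the interview | Parent | Yes, described as reaching local services | Yes, as an alternative |
| CES-D above 16 | Parent, from an information sheet | Yes | Yes, as an alternative |
| CES-D of 23 or above and a yes on self-harm | Interviewer, immediately | No | Yes, as the only contact |

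The option that does not depend on county is present at the two milder steps and absent at the gravest. No reason is given, so it looks like an oversight.

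**Step 2: the recruitment area.** The eligibility lists contain no county rule. Recruitment Methods and Setting both describe community outreach in Northeast Ohio. The only residence screen is Northeast Ohio, and it is stated only for people who respond through social media. The clinic letters, the discharge coordinators and the Cleveland Clinic referral route (Multi-Site Research section) state no residence limit. So the plan allows enrolment of parents who live outside Cuyahoga County, and visits to them there.

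**Step 3: resources elsewhere in the protocol.** A score of 23 exceeds 16, so a parent who reaches the crisis step should also receive the sheet listing 211. Adverse and Unanticipated Events adds a list of state-level and national agencies, with more specific resources if needed. That list is described for parents who get in touch asking for help. Neither resource is assigned to the interviewer's immediate call.

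**Step 4: when the step can operate face to face.** Table 1 schedules the CES-D at enrolment, 6 weeks, 3 months and 6 months. Research Design has face-to-face collection at T1, T3 and T4, which is 3 of the 4 time points. At T2 the survey link is emailed and parents are "contacted by phone for SF-12 survey with email reminders". The text does not say that the CES-D has been scored by that call, or that the caller asks the self-harm question.

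**Step 5: size.** The only depression rate given is 39.2% of 103 mothers scoring 16 or more in earlier work (Background). If that rate applied to the 123 parents to be enrolled, 0.392 × 123 = 48.2, or about 48 parents at one time point. This is an assumption, and 16 is the wrong cut-off for this step. The documents give no share at 23 or above, no share answering yes and no split by county, so the number affected cannot be derived.

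**The case against.** The strongest reply is that the harm depends on a fact the documents do not give. They do not state where the Mobile Crisis Team operates. The hotline's title includes information and referral, so it may direct calls from other counties. The parent will hold the 211 sheet, staff have the wider agency list, and nothing forbids calling 911. The additional files cited at the CES-D scoring step are not available here and may already hold contacts by county. Requests for help and expressions of distress are reported to the IRB and the safety monitoring committee and reviewed for protocol implications. The principal investigator, with the committee, decides on altering the study if more than two parents need referral to United Way First Call for significant distress. On this view, a county contact list belongs in staff procedures.

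Much of that stands. A reader might infer that the county team cannot respond elsewhere and that help would be delayed there. The documents do not support that reading, because neither the service area nor the handling of outside calls is stated. A reader might also infer that live contact is planned at all four CES-D time points, so that location could always be asked when the score is known. That is not supported either: the T2 call is stated only for the SF-12.

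What does not stand is that the other resources close the gap. The 211 sheet is for the parent to use, the agency list is not tied to this step, and committee review comes after the event. An interviewer should not have to improvise away from a written instruction at that moment.

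**Conclusion.** The mismatch is real and can be read directly from the text: one county-named contact, stated in two sections, for a trial that recruits across a wider region. It is minor. Delay outside the county is plausible but not demonstrated, its frequency is unknown, and the resources in other sections reduce the gap. The conclusion assumes only that some parents may live or be seen outside Cuyahoga County, which the plan allows. It would fall away if the sponsor confirmed that the team or its hotline serves the whole recruitment area, or that the additional files already give interviewers a contact by location. Estimates and error rates are unaffected. It is worth acting on because it concerns participant safety and costs almost nothing.

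**What to change.** In both sections, replace the single contact with wording such as: *the mobile crisis or emergency service covering the parent's location at the time of contact (in Cuyahoga County, the Mobile Crisis Team; elsewhere, that county's crisis service or 911)*. Have staff confirm the parent's location at whichever contact the self-harm question is asked; the wording then works however T2 is handled. Give interviewers a one-page list of crisis services by county or, if the additional files already contain one, cite them at this step.

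The cost is a wording change in two places, a short list to prepare and a minor IRB amendment. No staff, visits or procedures are added, and the place of each visit is already agreed with the parent.
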